## **3.2 Exclusion Criteria**

Participants meeting any of the following criteria are not eligible for study enrollment:

- 3.2.1 Prior allogeneic hematopoietic stem cell transplants.
- 3.2.2 For patients with acute myeloid leukemia, morphologically relapsed or refractory disease, as assessed by bone marrow aspirate and biopsy performed within 42 days prior to study entry, is exclusionary. For patients with myelodysplastic syndromes or chronic myelomonocytic leukemia, the presence of less than 5% myeloblasts is allowed on a bone marrow biopsy within 42 days prior to study entry.
- 3.2.3 History of other malignancy(ies) unless
  - the participant has been disease-free for at least 5 years and is deemed by the investigator to be at low risk of recurrence of that malignancy, or
  - the only prior malignancy was cervical cancer in situ and/or basal cell or squamous cell carcinoma of the skin
- 3.2.4 Known diagnosis of active hepatitis B or hepatitis C
- 3.2.5 Current or history of congestive heart failure New York Heart Association (NYHA) class 3 or 4, or any history of documented diastolic or systolic dysfunction (LVEF < 40%, as measured by MUGA scan or echocardiogram)
- 3.2.6 Current or history of ventricular or life-threatening arrhythmias or diagnosis of long-QT syndrome
- 3.2.7 QTc interval (i.e., Fridericia's correction [QTcF])  $\geq$  450 ms or other factors that increase the risk of QT prolongation or arrhythmic events (e.g., heart failure, hypokalemia, family history of long QT interval syndrome) at screening
- 3.2.8 Systemic uncontrolled infection

---

CONFIDENTIAL

This document is confidential. Do not disclose or use except as authorized.

- 3.2.9 Uncontrolled intercurrent illness that would limit compliance with study requirements.
- 3.2.10 HIV-positive participants on combination antiretroviral therapy are ineligible because of the potential for pharmacokinetic interactions with study drug. In addition, these participants are at increased risk of lethal infections when treated with marrow-suppressive therapy.

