## 5.2 Pre-Treatment Criteria

### 5.2.1 Cycle 1, Day 1

Treatment may begin at any time between day 30 and day 90 following stem cell transplantation. However, at time of treatment start, it must be ensured that:

- The patient has continued willingness and interest in participating in the study.
- Chimerism studies reveal that  $\geq 70\%$  of blood or bone marrow cells, or of the CD33 expressing fraction, are of donor origin,
- There is no acute graft versus host disease (GVHD), requiring an equivalent dose of  $\geq 0.5\text{mg/kg/day}$  of prednisone within one week of starting ivosidenib, or have escalation of systemic immunosuppression in terms of increase of corticosteroids or addition of new agent/modality within two weeks of starting ivosidenib.
- There is no evidence of relapsed/recurrent/residual disease.
- There is no systemic infection requiring IV antibiotic therapy within 7 days of starting ivosidenib

Prior to the start of ivosidenib administration, the participant must have adequate hematological function, defined as:

- ANC  $\geq 1000/\mu\text{L}$
- Platelets  $\geq 50,000/\mu\text{L}$

and adequate organ function defined as

- Direct bilirubin level  $< 2.0 \text{ mg/dL}$
- AST (SGOT), ALT (SGPT) and Alkaline phosphatase  $< 3x$  institutional upper limit of normal (ULN)
- Presence of congestive heart failure, defined by New York Heart Association (NYHA) criteria as class 3 or 4
- Calculated creatinine clearance  $\geq 40 \text{ mL/min}$  (Cockcroft-Gault formula)

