### 6.5 QT Prolongation

Subjects may be at increased risk for the development of QT prolongation when treated with ivosidenib in combination with fluoroquinolones, azole antifungal agents, or serotonin (5-HT3) antagonists. Investigators must be vigilant and attempt to avoid administering concomitant medications associated with QT prolongation whenever possible, and if no other therapeutic options are available, monitor subjects receiving study treatment with the combination of these drugs. They should evaluate ECG and electrolytes (including potassium, magnesium, and calcium) at least weekly for the first cycle of therapy. Vigilance is particularly important in

CONFIDENTIAL

This document is confidential. Do not disclose or use except as authorized.

subjects presenting with nausea, vomiting, or diarrhea. Systemic administration of a moderate or strong CYP3A4 inhibitor requires careful monitoring of QTcF.

Participants who experience QTcF prolongation to  $> 480$  msec (Grade  $\geq 2$ ) while treated with ivosidenib should be promptly evaluated for causality of the QTc prolongation and managed according to the following guidelines:

- Levels of electrolytes (potassium, calcium, and magnesium) should be checked and supplementation given to correct any values outside the normal range.
- Concomitant therapies should be reviewed and adjusted as appropriate for medication with known QT prolonging effects.
- ECGs should be conducted at least weekly for 2 weeks following QTcF reduction  $\leq 480$  msec.

If no other cause is identified and the investigator believes it is appropriate, particularly if QTc remains elevated (after above measures have been implemented, or as determined by the investigator), ivosidenib dosing may be interrupted. An ECG should be rechecked in approximately 1 week after the QTcF prolongation was first observed or more frequently as clinically indicated.

If QTc has recovered or improved and the investigator believes it is safe to do so, re-challenge with ivosidenib should be considered if held.

If Grade 2 (QTcF  $> 480$  and  $\leq 500$  msec), the dose of ivosidenib may be reduced without interruption of dosing. The ivosidenib dose may be re-escalated to the prior dose in  $\geq 14$  days after QT prolongation has decreased to  $\leq$  Grade 1.

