## 10. STUDY CALENDAR

Pre-study screening evaluations are to be conducted within 42 days prior to registration. All cycles are 28 days in duration. There are no rest periods between cycles. Whenever possible, the study visit should occur on the scheduled visit day. A ± 5-day window is allowed in order to accommodate participants' schedules.

	Screening	Pre-Treatment 	Cycle 1			Pre-Cycles 2, 3	Pre-Cycles 4, 5, 7, 8, 10, 11	Pre-Cycles 6, 9, 12	Relapse	End of Treatment 	Follow-Up 
	Pre-HSCT	D-14	D1 	D8	D15						
Informed Consent	X										
Medical History	X	X									
Physical Exam	X	X	X	X	X	X	X	X	X	X	
Vitals (BP, HR, RR)	X	X	X	X	X	X	X	X	X	X	
Performance Status	X	X	X							X	
12-lead ECG	X		X	X	X	X	X	X	X	X	
Echocardiogram or MUGA scan	X										
CBC w/ diff	X	X	X	X	X	X	X	X	X	X	
Chemistries 	X	X	X	X	X	X	X	X	X	X	
GVHD assessment 		X	X	X	X	X	X	X		X	X
Peripheral blood chimerism			X					X	X	X	
Coagulation parameters (PT, PTT, INR, D-dimer, fibrinogen)	X	X	X	X	X	X	X	X	X	X	
Pregnancy Test 	X		X			X	X	X		X	
Bone Marrow Biopsy and Aspirate 	X	X						C6 and C12 only	X		
Adverse Event Evaluation	X		X	X	X	X	X	X	X	X	X
Blood for correlative studies (2-HG, NGS)		X		X	X	X			X		

CONFIDENTIAL

This document is confidential. Do not disclose or use except as authorized.

WGS)											
Survival											X
Disease Assessment 							C6 and C12 only	X			
New Antineoplastic Therapy 											X

 Pre-treatment evaluations are to be conducted within 14 days prior to start of protocol therapy. Pre-treatment bone marrow biopsy is to be conducted after neutrophil engraftment (defined as ANC  $\geq 1000/\mu\text{L}$ ). In the event that the participant's condition is deteriorating, laboratory evaluations should be repeated within 48 hours prior to initiation of the next cycle of therapy.

 Any evaluations that are required at both pre-treatment and Cycle 1 Day 1 do not need to be repeated on Cycle 1 Day 1 if they were done in the previous 7 days.

 Cycle 1 Day 1 assessments must be performed prior to administration of ivosidenib. Patients must fulfill Day 1 laboratory criteria as outlined in Section 5.2.1.

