 Chemistries include sodium, potassium, calcium, magnesium, phosphorus, chloride, blood urea nitrogen (BUN), total bilirubin, direct bilirubin, creatinine, albumin, total protein, alkaline phosphatase, alanine aminotransferase (ALT), aspartate aminotransferase (AST), lactate dehydrogenase (LDH).

 Symptoms of both acute and chronic GVHD should be assessed. Criteria are listed in section 11.2 and 11.3.

 Pregnancy test is only required for women of childbearing potential. This must be done within 7 days prior to study drug administration at each cycle.

 An End of Treatment visit should occur within 5 days of the last dose of study drug. If the required evaluations have been performed as part of another study visit, they do not need to be repeated.

 Disease assessment will be based on modified IWG criteria or other appropriate response criteria for the malignancy being studied.

 Follow-up data will be collected every 3 months for 24 months from the start of treatment until participant withdrawal, change of therapy following conclusion of study treatment, removal from study, or death. These evaluations may occur at an outside hospital or clinic, as long as documentation is received by the study site for reporting purposes.

 All new therapies administered after the last dose of ivosidenib are to be captured during follow-up.

 Post-transplant bone marrow biopsies and aspirates are allowed a  $\pm 1$  month window

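### Section 5.2.1 sets no QTcF limit for treatment start, so no value of the pre-dose Cycle 1 Day 1 ECG stops the first dose

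*Combined protocol and SAP*

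**What the plan says.** **Enrolment.** Exclusion 3.2.7 removes anyone with a QTcF of 450 ms or more, or with other factors that raise QT risk: "e.g., heart failure, hypokalemia, family history of long QT interval syndrome) at screening". The Study Calendar (Section 10) labels the screening column as pre-HSCT and asks for screening within 42 days before registration. Inclusion 3.1.3 likewise enrols people whose transplant is still to come.

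**Treatment start.** Section 5.2.1 lets ivosidenib begin between day 30 and day 90 after transplant and opens its list of conditions with "However, at time of treatment start, it must be ensured that". The list covers willingness, chimerism, acute GVHD, disease status, infection, ANC, platelets, direct bilirubin, liver enzymes, an NYHA heart-failure line and creatinine clearance. Neither QTcF nor any electrolyte appears.

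**Measurement.** The calendar schedules a 12-lead ECG at screening and on Cycle 1 Day 1, but not at the pre-treatment visit. Footnote 3 says "Cycle 1 Day 1 assessments must be performed prior to administration of ivosidenib" and then "Patients must fulfill Day 1 laboratory criteria as outlined in Section 5.2.1". Footnote 4 begins "Chemistries include sodium, potassium, calcium, magnesium, phosphorus, chloride", so the relevant electrolytes are measured.

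**On treatment.** Section 6.5 acts when QTcF rises above 480 ms in participants who, "while treated with ivosidenib should be promptly evaluated for causality of the QTc prolongation and managed according to the following guidelines". Above 480 and up to 500 ms the dose may be reduced without a pause. Above 500 ms dosing is interrupted.

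**The concern.** The only QTcF limit that applies before dosing is checked before conditioning, transplant and whatever antifungals, quinolones or antiemetics follow. Section 5.2.1 shows that the authors did not regard pre-transplant values as sufficient, since it repeats most of the laboratory limits at treatment start. Of the QT risk factors named in 3.2.7, heart failure is carried into 5.2.1, but the QTcF itself is not.

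QT prolongation is a listed expected reaction to ivosidenib (7.1.1, 1-10%), and 5.5 links higher exposure to QTc prolongation. Section 8.1.1 reports roughly 2-fold accumulation, with steady state within 15 days, so the Day 1 ECG is read before exposure has built up. The plan obtains that ECG and does not say what reading defers the first dose. Two sites could treat the same reading differently, and both would comply with the protocol.

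**Working it through.** The plan gives no figure to reproduce, so the check sets the rules side by side and adds simple arithmetic.

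**Inputs.** 450 ms (3.2.7); 480 and 500 ms, and return to within 30 ms of baseline (6.5); screening within 42 days before registration, Day 8 visit, ±5-day window (Section 10); start on day 30-90 (5.2.1).

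**Step 1: which enrolment limits return at treatment start.**

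| Enrolment limit | Repeated in 5.2.1? |
|---|---|
| ANC, platelets | Yes |
| Direct bilirubin, AST, ALT, alkaline phosphatase | Yes |
| Creatinine clearance | Yes |
| Heart failure, NYHA class 3-4 | Addressed |
| QTcF below 450 ms | No |

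Footnote 3 does not fill the gap. It sends the reader back to the laboratory criteria of 5.2.1, and an ECG is not a laboratory test.

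**Step 2: what the rules say for each reading.**

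| QTcF | At enrolment (3.2.7) | First dose (5.2.1) | On drug (6.5) |
|---|---|---|---|
| 450 to 480 ms | Excluded | No rule | No action |
| Above 480 to 500 ms | Excluded | No rule | Prompt evaluation, optional reduction |
| Above 500 ms | Excluded | No rule | Mandatory interruption |

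**Step 3: age of the screening ECG at first dose.** Screening precedes transplant and dosing starts no earlier than day 30, so the minimum is more than 30 days. If registration falls on the day of transplant (assumption), the maximum is 42 + 90 = 132 days. It is longer if registration comes earlier, because the documents set no maximum from registration to transplant.

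**Step 4: room before the interruption level.** At the highest whole-millisecond value that 3.2.7 admits: 500 − 449 = 51 ms. At an illustrative Day 1 value of 490 ms: 500 − 490 = 10 ms. The next calendar ECG is on Day 8, and 8 − 1 = 7 days later. The calendar's "5-day window is allowed in order to accommodate" schedules makes that 7 − 5 = 2 to 7 + 5 = 12 days. Sections 5.5 and 6.5 ask for ECGs at least weekly in cycle 1 with interacting drugs, so 12 days is the outer edge and would not apply to those participants.

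**Step 5 (minor): baseline in 6.5.** The available text does not say which ECG is the baseline. With illustrative values of 440 ms at screening and 490 ms on Day 1, the resumption ceiling is 440 + 30 = 470 ms or 490 + 30 = 520 ms. The second lies 520 − 500 = 20 ms above the mandatory hold. The two rules conflict only when the baseline exceeds 500 − 30 = 470 ms.

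**The case against.** **The physician has a current reading.** The Day 1 ECG must precede dosing. The carry-over in footnote 2 ("do not need to be repeated on Cycle 1 Day 1 if they were done in the previous 7 days") covers only tests due at both the pre-treatment visit and Day 1, so it applies to chemistries and not to the ECG. Section 5.5.1 calls for vigilance, 6.5 for avoiding QT-prolonging drugs where possible, 6.4 for 250 mg with strong CYP3A4 inhibitors, and 4.1 and 4.3 for discussing treatment delays with the principal investigator. All of this stands and lowers the risk. None of it states a value at which the first dose waits.

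**450 ms is an enrolment limit.** Section 6.5 takes no action up to 480 ms and lets dosing continue up to 500 ms. A 450 ms limit at start would hold back people whose QTcF the plan accepts once they are on drug. This stands as an argument about which number to choose, and the sponsor should be free to justify one above 450 ms. It does not explain having none, least of all above 500 ms.

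**Other limits are not repeated either.** LVEF and performance status are also absent from 5.2.1. That is true, but neither has the direct link to a listed reaction of this drug that QTcF has.

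**Stronger readings that the documents do not support.**

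- A reader might infer that an electrolyte limit was dropped. Section 3.2.7 names hypokalemia only as an example and gives no number, so there was no numeric limit to carry forward.
- A reader might infer from the baseline wording that 6.5 directs dosing above 500 ms. Resumption there is permissive, at a reduced dose and subject to investigator judgment. The conflict largely disappears once a start limit exists, and it concerns participants at 500 mg, since no study dose lies below 250 mg.
- A reader might apply the listed 1-10% to 22 participants (22 × 0.01 = 0.22 to 22 × 0.10 = 2.2) as the number affected. That would count QT prolongation of any kind, not people who start above a limit.

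**Conclusion.** The point holds for QTcF and should be corrected. As written, the start rules permit a first dose of a drug with a listed QT risk at a reading that bars enrolment and, above 500 ms, would stop dosing in someone already on treatment. The ECG needed to prevent this is already scheduled at the right time.

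The size cannot be put as a number of participants, because the documents do not give how often Day 1 QTcF is 450 ms or more. What can be stated is that there is no rule in any band from 450 ms upward, and that the ECG carrying the limit is more than 30 days old at first dose (up to about 132 days under the registration assumption). The electrolyte and baseline matters are secondary.

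This is a gap in safety eligibility, not a statistical error. A reader might infer that it distorts the DLT count or the RP2D. The documents give no basis for that, and it is not claimed.

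The conclusion rests on 5.2.1 and the calendar footnotes, which are complete. Parts of the public text in 5.5 and around 6.6 were unavailable and are assumed not to contain a start limit.

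**What to change.** Add to 5.2.1: the pre-dose Cycle 1 Day 1 QTcF must be below 450 ms as in 3.2.7, or meet another limit that the sponsor justifies and that is no looser than the 480 ms action level of 6.5. Low potassium, magnesium or calcium is corrected first, and the ECG may be repeated at any time within the day 30-90 window.

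As a minor clarification to 6.5, name that Day 1 ECG as the baseline and state that dosing does not resume while QTcF is above 500 ms.

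**Cost.** Two or three sentences in an amendment and no additional scheduled tests, since repeat ECGs arise only when the first reading is too high. Some starts will be delayed. A few participants may stay above the limit through day 90 and never start, for example those who need an azole. At the planned 1-2 patients per month, each lost start costs 1/2 = 0.5 to 1/1 = 1 month of accrual. Section 13 already commits to reporting the proportion who consent but never start, so this loss would be visible.

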### **3.3 Inclusion of Women and Minorities**

Both men and women of all races and ethnic groups are eligible for this trial.

## **4. REGISTRATION PROCEDURES**

### **4.1 General Guidelines for DF/HCC Institutions**

Institutions will register eligible participants in the Clinical Trials Management System (CTMS) OnCore. Registrations must occur prior to the initiation of protocol-specific therapy. Any participant not registered to the protocol before protocol-specific therapy begins will be considered ineligible and registration will be denied.

An investigator will confirm eligibility criteria and a member of the study team will complete the protocol-specific eligibility checklist.

Following registration, participants may begin protocol-specific therapy. Issues that would cause treatment delays should be discussed with the Overall Principal Investigator (PI). If a participant does not receive protocol-specific therapy following registration, the participant's registration on the study must be canceled. Registration cancellations must be made in OnCore as soon as possible.

### **4.2 Registration Process for DF/HCC Institutions**

DF/HCC Standard Operating Procedure for Human Subject Research Titled *Subject Protocol Registration* (SOP #: REGIST-101) must be followed.

### **4.3 General Guidelines for Other Investigative Sites**

Eligible participants will be entered on study centrally at Massachusetts General Hospital by the Coordinating Center. All sites should contact the Coordinating Center to verify treatment availability.

Following registration, participants may begin protocol treatment. Issues that would cause treatment delays should be discussed with the Principal Investigator/Sponsor. If the subject does not receive protocol-specific therapy following registration, then the subject must be taken off-study in the CTMS (OnCore) with an appropriate date and reason entered.

---

CONFIDENTIAL

This document is confidential. Do not disclose or use except as authorized.

#### **4.4 Registration Process for Other Investigative Sites**

To register a subject, the following documents should be completed by the participating institution and forwarded to the Coordinating Center:

- Copy of source documentation for inclusion/exclusion criteria and screening procedures, including but not limited to
  - Pathology report
  - Medical history and physical exam
  - Laboratory reports
  - Radiology results/reports
  - Echo or MUGA report
  - ECG report
  - Concomitant medication list
- Demographics information
- Signed study consent form and HIPAA authorization form (if separate from consent)
- Study Entry Note and documentation of consent process
- Eligibility checklist

The Coordinating Center will review the above documentation to verify eligibility and consent. To complete the registration process, the Coordinating Center will follow DF/HCC Standard Operating Procedure for Human Subject Research Titled *Subject Protocol Registration* (SOP #: REGIST-101) and register the participant on the protocol. Once registered, a confirmation email with the participant study number, and if applicable the dose treatment level, will be sent to the participating site.

**NOTE:** Registrations can only be conducted by the Coordinating Center during the business hours of 8:30 AM and 5:00 PM Eastern Standard Time (or Eastern Daylight Time when applicable), Monday through Friday. A complete registration packet, including all documents listed above, must be received at least 1 business day *prior to* the anticipated registration to ensure adequate review. Same day treatment registrations will only be accepted with prior notice and discussion with the Coordinating Center.

**Treatment may not begin without confirmation from the Coordinating Center that the participant has been registered.**

### **5. TREATMENT PLAN**

#### **5.1 Treatment Regimen**

Ivosidenib will be administered orally every day for 28 consecutive days, defined as a treatment cycle. Appropriate dose modifications are described in Section 6. Reported adverse events and potential risks are described in Section 7. No investigational or commercial agents or therapies other than those described below may be administered with the intent to treat the participant's myeloid malignancy.

---

CONFIDENTIAL

This document is confidential. Do not disclose or use except as authorized.

The starting dose of ivosidenib (AG-120) will be 500mg orally daily. After 3 (or 6) participants are treated at 500mg daily, if this dose is tolerated, then an additional 10 participants will be treated at 500mg daily. If the 500mg daily dose is NOT tolerated in the initial cohort of participants, then the dose will be decreased to 250mg daily. If 250mg daily is tolerated, then an additional 10 participants will be treated at 250mg daily. The only doses studied will be 500mg daily and 250mg daily (the latter, if necessary).

The first cohort will consist of three participants. After the third participant is enrolled to the cohort, enrollment will be put on hold until all three participants have completed the first 28-day cycle. The period for dose-limiting toxicity (DLT) evaluation is the first 28-day cycle. Individual participants must receive at least 50% of the dosing to be DLT evaluable for that cohort. If this criteria is not met, the patient in that dose-escalation cohort may be replaced.

If one of three participants in a cohort experiences a DLT, then an additional 3 participants will be observed at that dose. The recommended phase 2 dose (RP2D) is defined as the highest dose level at which 0 or 1 of six participants experiences a dose-limiting toxicity.

Dose Escalation Schedule	
Dose Level	Dose of Ivosidenib
Level 1	250mg daily
Level 2 – Starting Dose	500mg daily

Once the RP2D is defined, an additional 10 participants will be enrolled at that dose.

If 250mg daily dosing is not tolerated, then the study will end without expansion.

If the overall study is dose decreased to 250mg daily and there are still any participants receiving 500mg daily ivosidenib, those participants may continue to receive 500mg ivosidenib unless/until they develop a toxicity that requires a dose-reduction.

The participant will be required to maintain a medication diary of each dose of medication. He/she should record relevant information regarding study drug dosing in the diary (e.g. confirmation that each dose was taken, reasons for missed doses). The medication diary will be returned to clinic staff at the end of each cycle.

